Rationale	
Open questions are still needed to be answered:
 
 - In the exclusive radiotherapy scenario, does ENI produce an overall or biochemical relapse free survival advantage over prostate only radiotherapy for intermediate/high/very high-risk cases? - If ADT is added to prostate only radiotherapy, in intermediate/high/very high-risk cases, ENI is any longer needed?

	
 - Is ENI, associated or not to ADT, linked with an OS or bRFS survival advantage in patients submitted to adjuvant postsurgical prostate radiotherapy? - Additional toxicity due to the larger volumes treated might be reduced by more sophisticated radiotherapy techniques when ENI is added to prostate? - How many Radiation Oncology centers use ENI to treat patients with intermediate/high/very high-risk prostate cancer, with or without ADT? - The data obtained from the present observational study will be helpful for designing a subsequent randomized controlled trial.
End-points	
Primary:
 
 - Overall survival; 
Secondary:
 
 - Cause-specific (CSS) and Biochemical Relapse Free survival (bRFS); - acute and late toxicity evaluation (rectal, bladder, bowel toxicity, according to CTCAE v.4 scale); - Quality of Life deterioration (according to the UCLA-PCI scale).
Study design	
This is a prospective, multicenter, observational cohort study aimed to describe the advantage/disadvantage of different treatments of patients with intermediate/high/very high risk prostate cancer, through a web-based database.
 
The study will include all consecutive patients affected by intermediate, high or very high-risk prostate cancer that fit to the inclusion criteria and who are evaluated at each Centre involved in the study. Patients may have already undergone or not to radical prostatectomy and/or pelvic lymphadenectomy.
 
Phase 1: Establishment of the network of Centers involved in the study Phase 2: Activation and recruitment of eligible cases Phase 3: Follow-up (1,3,6,12/18,24/30/36 months)

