Toxicity	NCI Common Terminology Criteria for Adverse Events (CTCAE) version 4 for adverse event (AE) reporting. The CTCAE version 4 is identified and located on the CTEP web site at: http://ctep.cancer.gov/protocolDevelopment/electronic_applications/ctc.htm
Quality of Life	Quality of life and complications due to prostate cancer (Italian UCLA-PCI) General quality of life (SF-12 Standard V1)

Background

The extent of the problem

Prostate cancer (PCa) is the most common male malignancy in the United States and the rest of the Western world and its incidence is rising also in Asia, causing some concerns for public health [1, 2]. In Italy prostate cancer is in the third place of the cancer mortality scale (8% of all cancer related deaths) even if a constant, though moderate, annual decrease (-1.8%) has been observed for over twenty years [3] as well as a consequent increase in overall survival [4]. Despite these data, still now, in the post PSA era, current estimates indicate that high-risk disease accounts for 15% of all PCa diagnoses in the United States [5] and even more in the low-PSA screening regions.

Radiotherapy for prostate cancer: some open questions

Several modalities, alone and/or in combination, have been advocated to treat patients with intermediate/high/very high risk PCa [6], but universally accepted consensus guidelines are still lacking. Mounting evidence supports the use of a multimodality approach to treat locally advanced prostate cancer and in particular the combination of Radiation Therapy (RT) with Total Androgenic Deprivation (ADT); adjuvant post-surgical RT is also needed in many cases submitted to radical prostatectomy (RP) because of unexpected extracapsular invasion or microscopically involved margins. In both cases, some issues are still present regarding RT: volumes of interest, total dose, radiation techniques and fractionation.

The efficacy of elective nodal irradiation and the issue of its association with hormonal manipulation in the context of radical exclusive radiotherapy for prostate cancer

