In summary, the study aims at the definition of survival, toxicity and QoL data in a representative sample of intermediate, high and very high risk prostate cancer patients consecutively recruited in Italian Radiation Oncology Centres over two years. Parameters considered will be OS, CSS and bRFS, toxicity (rectal, bladder, bowel toxicity, according to CTCAE v.4 scale) and QoL (according to the SF-12 scale and UCLA-PCI scale). Primary end point will be OS. Secondary endpoints will be CSS, bRFS, gastrointestinal and genitourinary toxicity, QoL deterioration.

Study Design

This is a prospective, multicenter, observational cohort study aimed to describe the advantage/disadvantage of different treatments of patients with intermediate/high/very high risk prostate cancer, through a web-based database.

Study Duration

The recruitment period, taking into account the needed sample size (*v.infra*) will be of two years, followed by three-year follow up period for each patient, with an accrual of at least 400-500 patients.

Population, Procedures

The study will include all consecutive patients affected by intermediate, high or very high-risk prostate cancer that fit the inclusion criteria and who are evaluated at each Centre involved in the study. Patients may have already undergone or not to radical prostatectomy and/or pelvic lymphadenectomy.

Inclusion criteria

- Men older than or aged 18 years;
- Histologically confirmed intermediate, high or very high risk prostate cancer patients (NCCN classification: Intermediate Risk T2b and T2c or Gleason Score 7 or PSA value between 10 and 20 ng/mL; High risk: T3a or Gleason score 8-10 or PSA > 20 ng/ml; Very high risk: T3b-T4 or patients with multiple adverse risk factors reported in the high risk category that may be shifted in the very high risk group
- Patients eligible for -and actually submitted to- radical radiotherapy treatment (+/- androgen deprivation) or adjuvant radiotherapy treatment after surgery (radical prostatectomy +/- pelvic lymphadenectomy);
- No other synchronous or previous malignant tumor other than skin basal cell carcinoma;
- Patients able to understand and sign the appropriate informed consent;
- Patients able to fill the QoL questionnaire;

Exclusion criteria

- Patients aged less than 18;

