- Treatment : type of treatment, start date, PSA value before treatment; if surgery type of surgery and pathological TNM, margins, Gleason Score, number of positive lymph nodes; if external RT (intent, modality, technique, dose/fraction, volumes, concomitant hormonal therapies); if brachytherapy (type, intent, dose); if hormone therapy (type of drugs, start and end date, total duration);
- Acute and late toxicities;
- Biochemical Relapse with PSA value and date of last PSA;
- Quality of life and symptoms due to prostate cancer (Italian UCLA-PCI);
- General quality of life SF-12.

Toxicity and response evaluation

The enrolled patients will undergo the first follow up visit one month after the end of radiotherapy. On that occasion, clinical examination will be performed and previously prescribed blood tests, if required, will be evaluated. Genitourinary and gastrointestinal toxicity due to radiation therapy for prostate cancer will be reported according to the NCI Common Terminology Criteria for Adverse Events (CTCAE) version 4 for adverse event (AE) reporting. The CTCAE version 4 is identified and located on the CTEP web site at:

http://ctep.cancer.gov/protocolDevelopment/electronic_applications/ctc.htm [48]

In addition, a Case Report Form (CRF) will be completed (see Attachment 2), regarding:

- Technical characteristics of the radiation treatment (dose, volume, technique, association or not with hormonal therapy);
- Quality of life and complications due to prostate cancer (according to Italian UCLA-PCI) [45, 46];
- General quality of life (SF-12 Standard V1) [47].

Thereafter patients will be evaluated at 3-months, 6-months and 12-months after the end of radiotherapy, and then every 6 months for at least 24 months. During all those scheduled follow up visits, PSA level (jointly with testosterone, in case of association with hormonal therapy) and

previously prescribed blood texts if required, will be evaluated. Patients will undergo clinical examination, and genitourinary and gastrointestinal toxicity will be assessed according to the CTCAE v4.0 classification scale). In addition, a CRF (see Attachment 3) will be completed at each visit, regarding:

- Survival status (mortality, date and cause of death) or exit from the study;
- If macroscopical recurrence or disease progression occurred, the radiological exams (if performed);
- Further treatments received/planned after radiotherapy;
- The last available PSA;

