- Quality of life and complications due to prostate cancer (Italian UCLA-PCI) [45, 46];
- General quality of life (SF-12 Standard V1) [47].

The Italian UCLA-PCI and SF-12 Standard V1 questionnaires reported in Attachment 2 and Attachment 3 [45, 46, 47] will be given by the referring physician and self-compiled by patients in physician's absence, eventually with the help of a nurse if necessary; thereafter, the referring physician will insert the data to the database.

Data Collection, Confidentiality

Data will be collected through an *ad hoc* web based software, built to guarantee:

1. Respect of the Italian laws and of the international rules about GMP and privacy, according also to the general principles fixed by the Helsinki declaration and its subsequent updates;
2. The anonymization of the patient records;
3. The possibility for each participating Center to have unrestricted access to its own data;
4. The restriction of the access to the full dataset composed by the sum of the records provided by the single Centers; this will be allowed only after the authorization of the PI and the Study Coordinator. Once the study will be completed, access to the whole database will be possible only after having obtained the authorization of the AIRO President in charge and of the AIRO Board;
5. The safe storage of the data, along with that of the previous AIRO-PCSG studies, along with.

The use of the software will be elucidated to the single participating Centers in *ad hoc* start up

meetings, to guarantee an appropriate and homogeneous data collection; a tool bar will however be devised, to automatically verify inconsistencies in the data collected.

Statistical Considerations

Sample size

From previous experiences of the AIRO PCSG [49, 50], at least 15-20 Radiotherapy Centers from different regions of the country will be able to participate to the study. It is conceivable an accrual of at least 400-500 patients within 2 years and a further follow up of at least 3 years for each patient. For intermediate and high risk patients, an overall survival at 5 years of 0.8 has been previously reported (RTOG 94-13) [51]. According to the primary end-point of the study, a sample size of 400 patients will allow to estimate a 5-year survival of 0.8 with 95% confidence interval of 0.76-0.84 [52].

Statistical Analyses

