	2 . Yes, monolateral
	3 . Yes, bilateral
Pathological TNM after surgery	T __ N __ M __
Margins	1 R0
	2 R1
	3 R2
Gleason Score after surgery	__ + __ = __
Pre-treatment PSA __ ng/mL	
PSA date	__ / __ / __ day month year

SF-12 STANDARD ITALIAN VERSION

(Apolone G et al. 2001)

	Excellent	Very good	Good	Fair	Poor
1 In general, you would say that your health condition is:	1	2	3	4	5
The following questions regard some activities you might do during a typical day. Does your health condition actually limit you in doing these activities?					
	Yes, it limits a lot	Yes, it limits a little	No, it does not limit at all		
2 Activities of moderate physical effort , such as moving a table , using the vacuum cleaner , playing bowls or a riding a bicycle	1	2	3		
3 Climbing several flights of stairs	1	2	3		
During the last 4 weeks have you had the following problems at work or during other daily activities, because of your physical health condition?					
	Yes	No			
4 Accomplished less than you would like	1	2			
5 You had to limit certain kinds of occupation or other activities	1	2			
During the last 4 weeks have you had the following problems at work or during other daily activities, because of your emotional state (such as feeling depressed or anxious)?					
	Yes	No			
6 Accomplished less than you would like	1	2			
7 You did not do work or other activities as carefully as usual	1	2			
	Not at all	A little bit	Moderately	Quite a bit	Not at all
8 During the last 4 weeks , How much has pain hindered your usual work (at home and outside)?	1	2	3	4	5
How long during the last 4 weeks have you felt					
	All of the time	Most of the time	A good bit of time	Some of the time	A little of the time
9 calm and serene?	1	2	3	4	5
10 full of energy?	1	2	3	4	5
11 discouraged and sad	1	2	3	4	5
	All of the time	Most of the time	A good bit of time	Some of the time	A little of the time
12 During the last 4 weeks , how long have your physical health condition or your emotional state interfered with your social activities, with family, with friends?	1	2	3	4	5

COMPLICATIONS DUE TO PROSTATE CANCER
ITALIAN UCLA PROSTATE CANCER INDEX
(Gacci M et al, 2005)

URINARY FUNCTION

This session regards the urinary routine. Please consider only the last 4 weeks.

1. Over the LAST 4 WEEKS, how often have you leaked urine?
 - 1 Every day.
 - 2 About once a week
 - 3 Less than once a week
 - 4 Not at all.

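### SF-12 item 8 is printed with *Not at all* at both ends of its five-point scale in all three attachments, so codes 1 and 5 cannot be told apart by label

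*Combined protocol and SAP*

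**What the plan says.** The synopsis row on quality of life names the instrument: "General quality of life (SF-12 Standard V1". The SF-12 is in the pre-treatment CRF (Phase 2) and again in the follow-up CRF (Phase 3), where it is listed as "General quality of life SF-12". The summary that closes the Aims of the study defines the quality-of-life parameter as "QoL (according to the SF-12 scale and UCLA-PCI scale", and quality-of-life deterioration is a secondary endpoint. The End-points row of the synopsis is narrower: "Quality of Life deterioration (according to the UCLA-PCI scale".

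The section on toxicity and response evaluation describes how the forms are used: the "questionnaires reported in Attachment 2 and Attachment 3 [45, 46, 47] will be given by the referring physician and self-compiled by patients". The physician is absent while the form is filled in and then enters the data.

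The SF-12 page is reproduced in Attachments 1, 2 and 3. In each copy item 8 ("How much has pain hindered your usual work (at home and outside") is headed "Not at all A little bit Moderately Quite a bit Not at all" over codes 1 to 5. Items 9 to 11, and then item 12, are headed "All of the time Most of the time A good bit of time Some of the time A little of the time" over codes 1 to 5.

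The Statistical Analyses section gives no SF-12 scoring rule and no rule for items that are blank or ambiguous.

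**The concern.** The answers to a rating item must be distinct, and they must cover every state a patient can be in. Item 8 as printed fails on both counts: two codes share a label, and the most severe state has none.

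The two failures meet at code 5. A man with no interference can mark box 5 because its label says so. A man with the greatest interference can mark the same box because it follows *Quite a bit* in a rising series. The two extremes of the item can then share a stored value. A man whose pain does not interfere at either of two visits can also appear to move across the whole item.

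The data flow would not reveal this. The physician sees only the marked box. The automatic inconsistency check promised under Data Collection would not necessarily catch it either, since 1 and 5 are both permitted codes.

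**Working it through.** There is no sample-size, power or event figure to reproduce. The check is a comparison of printed labels with printed codes, item by item, in the three copies.

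**Item 8 (identical in Attachments 1, 2 and 3)**

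| Code | Printed label | Distinct? |
|---|---|---|
| 1 | Not at all | No, same as code 5 |
| 2 | A little bit | Yes |
| 3 | Moderately | Yes |
| 4 | Quite a bit | Yes |
| 5 | Not at all | No, same as code 1 |

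- Codes sharing a label: 2 of 5. Codes with an unambiguous label: 3 of 5 (2, 3 and 4).
- Largest gap between two records of the same reply: 5 − 1 = 4 codes, the full width of the item.
- Codes 1 to 4 rise in severity, so by position the fifth label should exceed *Quite a bit*. It does not.

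**Could reading the PDF have produced this?** A lost column leaves fewer labels; it does not put the first label again after the fourth. Item 8 has five labels over five codes in every copy. Item 1, the other five-answer item outside the frequency block, has five different labels in the same table. A reading error is therefore not a credible explanation for item 8.

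**Items 9 to 12 (identical in Attachments 1, 2 and 3).** Five labels stand over five codes, and the lowest frequency is *A little of the time*. If that is the true form, a man whose answer is never must choose the nearest label or leave the item blank. On items 9 and 10 (calm, energetic) the missing answer is the worst state; on items 11 and 12 (sad, socially limited) it is the best. Here, however, a lost sixth column would remove a label and its code together and leave exactly this pattern. The three copies share one layout and were read by one program, so their agreement is not independent evidence.

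**Count.** Established: 1 of 12 items. Conditional on the printed page really having five columns: 4 more, giving 5 of 12.

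**Exposure.** Phase 3 lists eight visits (1, 3, 6, 12, 18, 24, 30 and 36 months). With the baseline form that is 1 + 8 = 9 forms per patient. The title of Attachment 3 lists different months, but seven of them, so baseline, 1 month and seven later visits again give 1 + 1 + 7 = 9. For the planned 400 patients the ceiling is 9 × 400 = 3,600 forms, before deaths and losses. This counts forms carrying the item, not forms answered wrongly. The share answered ambiguously cannot be derived from the documents.

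**The case against.** The best counter-argument is that this page is not what patients see. The block is English text under a heading that calls it the Italian version, the cited source is the Italian edition, and the centres are Italian. The attachments contain other apparent translation slips: Phase 2 asks for the number of biopsy samples and of positive samples, while the corresponding fields in Attachment 1 ask about blood tests. A slipped label in item 8 fits that pattern, and the Italian form may be correct. This stands as a limit on certainty. It does not remove the point, because the protocol says the attachment questionnaires are the ones handed out and shows no other form.

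A reader might go further and infer that five of the twelve items cannot be scored correctly. The documents do not support that. For items 9 to 12 the missing option may be an artefact of PDF reading. Even if it is truly absent, those items fail only for men whose answer is never; the other answers keep ordered, distinct labels. In item 8, codes 2 to 4 remain usable.

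It is also fair to say that the 4-code gap is a worst case. It needs a man without pain interference to pass over the first box and mark the fifth.

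Finally, a reader might infer that the whole quality-of-life deterioration endpoint is compromised. The synopsis ties that endpoint to the UCLA-PCI alone, and only the body text adds the SF-12.

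**Conclusion.** The point holds for item 8. In all three attachments its end codes carry the same label and its most severe state has none, so data collected on the form as written are ambiguous at both ends of that item. For items 9 to 12 the finding is a conditional check, not an established defect.

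The reach is limited to the SF-12 part of a secondary endpoint. Overall survival, the UCLA-PCI and the other endpoints are not affected by this error.

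The conclusion assumes that the form given to patients, or the code list in the web database, matches the printed attachments. If both already follow the cited instrument, only the attachments need correcting. It rests on the printed answers being neither distinct nor complete. The published SF-12 answer set and scoring are not reproduced in the documents, so no comparison with them is made here.

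**What to change.** Before data entry:

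1. Compare the Italian form in use and the web-database codes, item by item, with the SF-12 Standard V1 that the protocol cites.
2. Correct the item 8 end label in Attachments 1, 2 and 3. Look at the original pages for items 9 to 12, and correct those items too if the zero-frequency answer is truly absent.
3. State in Statistical Analyses how the SF-12 is scored and how blank or ambiguous items are handled. The documents give no such rule.

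If forms were already completed as printed, flag every item 8 reply coded 1 or 5 as ambiguous, and report SF-12 results with and without those replies. If items 9 to 12 prove to lack the option, say so as a limitation.

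The cost is a corrected page in three attachments and one check of the code list, with no new data. The small downside arises only if the printed form was used: the analysis without codes 1 and 5 also discards replies that were given correctly, so it belongs beside the main SF-12 result as a sensitivity analysis.

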ATTACHMENT 2 – 1 MONTH FOLLOW UP

Date of starting treatment	_____ / _____ / _____ day month year
Date of ending treatment	_____ / _____ / _____ day month year
Pre-treatment PSA	_____ . _____ ng/mL

External Beam Radiation Therapy	
Aim of Radiation Therapy	1 Radical exclusive 2 Adjuvant 3 Salvage post-operative 4 Other, specify _____
Modality	1 IGRT 2 Non IGRT
Technique	1 3D-CRT 2 IMRT (step and shoot) 3 IMRT (volumetric) 4 SBRT (stereotactic body radiotherapy)
Technique-2	

	1 Sequential RT 2 SIB IMRT
Dose/fraction V1	__ , __ Gy
Total dose V1	__ , __ Gy
Dose/fraction V2	__ , __ Gy
Total dose V2	__ , __ Gy
Dose/fraction V3	__ , __ Gy
Total dose V3	__ , __ Gy
Rectum V25	Value
Rectum V50	Value
Rectum V60	Value
Rectum D50	Value
Rectum Dmax	Value
Bladder Dmax	Value
Bladder D50	Value
Bladder V50	Value
Bladder V70	Value
Penile Bulb Dmax	Value
Penile Bulb D90	Value
Small bowel V15 (contouring individual bowel loops)*	Value
Small bowel V45 (contour peritoneal space)*	Value
*contouring of the peritoneal space is required for all patients, optional contouring individual bowel loops	
Target volume V1	1 Prostate only 2 Prostate and basis of seminal vesicles 3 Prostate and seminal vesicles 4 Prostate plus pelvis (nodal volume) 5 Prostate and seminal vesicles and pelvis (nodal volume)

Target volume V2	1 Prostate plus pelvis 2 Nodal volume only 3 Prostate and seminal vesicles 4 Prostate and basis of seminal vesicles 5 Prostate only
Target volume V3	1 Nodal volume only 2 Prostate and seminal vesicles 3 Prostate and basis of seminal vesicles 4 Prostate only
Association with hormonal therapy	1 Radiotherapy alone 2 Radiotherapy and neoadjuvant hormonal therapy (before radiation therapy) 3 Radiotherapy and adjuvant hormonal therapy (after radiation therapy) 4 Radiotherapy and neoadjuvant + adjuvant hormonal therapy

Hormonal therapy					
Type of hormonal therapy	1	ADT			
	2	Periferic Antiandrogen If antiandrogen, specify the type: 1 Acetate ciproterone 2 Bicalutamide 3 Flutamide 4 Other, specify _____			
	3	If antiandrogen, specify the dose: _____			
	4	LHRH Agonist (or GnRH)			
	5	LHRH Antagonist (or GnRH)			
		Other, specify _____			
Date of starting hormonal therapy	day	/	month	/	year

Acute Toxicities

Rectal Acute Toxicity (Grade)

Date Tox.

Urinary Acute Toxicity (Grade)

Date Tox.

Small Intestine Acute Toxicity
(Grade)

Date Tox.

GI Acute Toxicity (small bowel)

(see Table 1)

select (1=G0, 2=G1, 3=G2, 4=G3, 5=G4, 6=Unknown)

Date yyyy-mm-dd

Rectal Acute Toxicity

select (1=G0, 2=G1, 3=G2, 4=G3, 5=G4, 6=Unknown)

Date yyyy-mm-dd

Urinary Acute Toxicity

select (1=G0, 2=G1, 3=G2, 4=G3, 5=G4, 6=Unknown)

Date

Late Toxicity bladder/ rectum

select (1=Yes, 2=No, 3=Unknown)

Date yyyy-mm-dd

Proctitis

select (1=G0, 2=G1, 3=G2, 4=G3, 5=G4, 6=I Unknown)

Date yyyy-mm-dd

Cystitis

select (1=G0, 2=G1, 3=G2, 4=G3, 5=G4, 6= Unknown)

Date yyyy-mm-dd

Impotence

select (1=No, 2=Yes pre RT, 3=Yes post RT, 4= Unknown)

Date yyyy-mm-dd

Incontinence

select (1=No, 2=Yes pre RT, 3=Yes post RT, 4=Unknown)

TABLE 1 – Toxicity

RECTAL/SMALL BOWEL Acute TOX

G0: No Toxicity

G1: Increased alvus frequency not requiring any treatment. Rectal pain or abdominal pain not requiring any painkillers

G2: Diarrhoea, mucositis, rectal pain or abdominal pain requiring painkillers

G3: Diarrhoea requiring parenteral supportive care, severe mucositis or haematological alterations requiring treatment. Abdominal distension

G4: Acute or subacute obstruction, fistula or perforation, haemorrhage requiring blood transfusion. Abdominal pain or tenesmus requiring ileostomy

BLADDER Acute TOX

G0: No Toxicity

G1: Low urinary tract symptoms (LUTS) and dysuria not requiring any treatment

G2: LUTS, dysuria and urgency requiring treatment or anaesthetics

G3: Severe LUTS, urgency, dysuria, pelvic pain or bladder spasms and haematuria

G4: Haematuria requiring blood transfusion, urinary obstruction, ulceration and necrosis

Late TOX PROCTITIS

G0: No Toxicity

G1: Mild rectal pain, Slight diarrhoea (less than 5 discharges). Small bleeding

G2: Diarrhoea (more than 5 discharges). Significant mucosal secretions and intermittent rectal bleeding

G3: Obstruction or haemorrhage requiring surgery

G4: Necrosis, perforation or fistula

Late TOX CYSTITIS

G0: No Toxicity

G1: Slight epithelial atrophy, small telangiectasia, microscopic haematuria

G2: Moderate LUTS, Intermittent macroscopic haematuria

G3: Severe LUTS and dysuria spread of telangiectasia. Frequent haematuria. Reduction in bladder capacity (less than 150 cc)

G4: Necrosis, bladder capacity reduced (less than 100 cc). Severe haemorrhagic cystitis

SF-12 STANDARD ITALIAN VERSION

(Apolone G et al. 2001)

	Excellent	Very good	Good	Fair	Poor
1 In general, you would say that your health condition is:	1	2	3	4	5
The following questions regard some activities you might do during a typical day. Does your health condition actually limit you in doing these activities?					
	Yes, it limits a lot	Yes, it limits a little	No, it does not limit at all		
2 Activities of moderate physical effort , such as moving a table , using the vacuum cleaner , playing bowls or a riding a bicycle	1	2	3		
3 Climbing several flights of stairs	1	2	3		
During the last 4 weeks have you had the following problems at work or during other daily activities, because of your physical health condition?					
	Yes	No			
4 Accomplished less than you would like	1	2			
5 You had to limit certain kinds of occupation or other activities	1	2			
During the last 4 weeks have you had the following problems at work or during other daily activities, because of your emotional state (such as feeling depressed or anxious)?					
	Yes	No			
6 Accomplished less than you would like	1	2			
7 You did not do work or other activities as carefully as usual	1	2			
	Not at all	A little bit	Moderately	Quite a bit	Not at all
8 During the last 4 weeks , How much has pain hindered your usual work (at home and outside)?	1	2	3	4	5
How long during the last 4 weeks have you felt					
	All of the time	Most of the time	A good bit of time	Some of the time	A little of the time
9 calm and serene?	1	2	3	4	5
10 full of energy?	1	2	3	4	5
11 discouraged and sad	1	2	3	4	5
	All of the time	Most of the time	A good bit of time	Some of the time	A little of the time
12 During the last 4 weeks , how long have your physical health condition or your emotional state interfered with your social activities, with family, with friends?	1	2	3	4	5

COMPLICATIONS DUE TO PROSTATE CANCER
ITALIAN UCLA PROSTATE CANCER INDEX
(Gacci M et al, 2005)

URINARY FUNCTION

This session regards the urinary routine. Please consider only the last 4 weeks.

1. Over the LAST 4 WEEKS, how often have you leaked urine?
 - 1 Every day.
 - 2 About once a week
 - 3 Less than once a week
 - 4 Not at all.
2. Which of the following best describes your urinary control during the LAST 4 WEEKS?
 - 1 No control whatsoever
 - 2 Frequent dribbling
 - 3 Occasional dribbling
 - 4 Total control
3. How many pads or adult diapers per day have you usually used to control leakage during the LAST 4 WEEKS?
 - 1 3 or more pads per day
 - 2 1-2 pads per day
 - 3 No pads
4. How big a problem, if any, has each of the following been for you?
Dripping urine or wetting your pants?
 - 0 No problem
 - 1 Very small problem
 - 2 Small problem
 - 3 Moderate problem
 - 4 Big problem
Urine leakage interfering with your sexual activity?
 - 0 No problem
 - 1 Very small problem
 - 2 Small problem
 - 3 Moderate problem
 - 4 Big problem
5. Overall, how big a problem has your urinary function been for you during the LAST 4 WEEKS?
 - 0 No problem
 - 1 Very small problem
 - 2 Small problem
 - 3 Moderate problem
 - 4 Big problem

BOWEL FUNCTION

The following section talks about all the bowel function and abdominal pain. Please consider only the last 4 weeks.

6. How often have you had rectal urgency (felt like you had to pass stool, but did not) during the LAST 4 WEEKS?
 - 1 More than once a day
 - 2 About once a day
 - 3 More than once a week
 - 4 About once a week
 - 5 Rarely or never
7. How much distress have your bowel movements caused you during the LAST 4 WEEKS?
 - 1 Severe distress

2 Moderate distress
 3 A little distress
 4 No distress

8. How often have you had crampy pain in your abdomen or pelvis during the LAST 4 WEEKS?
 1 Several times a day
 2 About once a day
 3 Several times a week
 4 About once this month
 5 Rarely or never

9. In particular, how big was the problem of bowel habits during the LAST 4 WEEKS?
 1 Big problem
 2 Moderate problem
 3 Little problem
 4 Very small problem
 5 No problem

SEXUAL FUNCTION

THE NEXT SECTION IS ABOUT YOUR SEXUAL FUNCTION AND SEXUAL SATISFACTION. MANY OF THE QUESTIONS ARE VERY PERSONAL, BUT THEY WILL HELP US UNDERSTAND THE IMPORTANT ISSUES THAT YOU FACE EVERY DAY. REMEMBER THAT YOUR ANSWERS TO THIS QUESTIONNAIRE WILL BE KEPT CONFIDENTIAL AND WILL BE USED ONLY FOR RESEARCH PURPOSES. PLEASE ANSWER HONESTLY ABOUT THE LAST 4 WEEKS ONLY.

10. HOW WOULD YOU RATE EACH OF THE FOLLOWING DURING THE LAST 4 WEEKS?

	Very poor	Poor	Fair	Good	Very good
A. Your ability to have an erection?	1	2	3	4	5
B. Your ability to reach orgasm (climax)	1	2	3	4	5

11. How would you describe the usual QUALITY of your erections?
 1 None at all
 2 Not firm enough for any sexual activity
 3 Firm enough for masturbation and foreplay only
 4 Firm enough for intercourse

12. How would you describe the FREQUENCY of your erections?
 1 I NEVER had an erection when I wanted one
 2 I had an erection LESS THAN HALF the time I wanted one
 3 I had an erection ABOUT HALF the time I wanted one
 4 I had an erection MORE THAN HALF the time I wanted one
 5 I had an erection WHENEVER I wanted one

13. Overall, how would you rate your sexual function during the LAST 4 WEEKS?
 1 Very poor
 2 Poor
 3 Fair
 4 Good
 5 Very good

14. Overall, how big a problem has your sexual function been for you during the LAST 4 WEEKS?
 1 No problem
 2 Very small problem
 3 Small problem
 4 Moderate problem
 5 Big problem

